## **I. Background:**

COVID-19, caused by the SARS-CoV-2 coronavirus, has resulted in over 1,290,000 deaths worldwide, with nearly 11 million cases and over 240,000 deaths in the US. The burden of COVID-19 in the US has fallen disproportionately on racial minorities and socioeconomically disadvantaged groups. For example, 30% of Chicago's population is Black, but 60% of COVID-19 deaths are among Black people. The Latinx community has also experienced a disproportionate burden of COVID deaths, both in Chicago and elsewhere. Social distancing remains a critical strategy, but may be particularly difficult for minority and disadvantaged populations, which have higher proportions of multigenerational households and essential workers who cannot avoid exposure to COVID-19. Despite the global need for effective biomedical strategies to prevent COVID-19, an effective and widespread vaccine could take a year or more.

It has recently been proposed that vitamin D deficiency may increase vulnerability to COVID-19 and vitamin D supplementation may be valuable in prevention and treatment. COVID-19 presents complex challenges with respect to immune function, requiring activation of innate immunity for prevention and modulation of adaptive immunity in treating inflammatory stages of the disease. In addition to its well-known roles in bone health, vitamin D activates innate immunity and suppresses excess inflammation in adaptive immunity, decreases acute respiratory infections and improves inflammatory conditions. A meta-analysis found viral respiratory infections decreased 70% in persons with vitamin D deficiency randomized to receive vitamin D and 10% in persons with "sufficient" levels. These findings motivate the hypothesis that vitamin D may be important in COVID-19.

Growing epidemiological evidence points to potential effects of vitamin D in COVID-19. Nearly half the US population is vitamin D deficient, with higher rates in older adults and African-Americans, Latinx individuals, and other racial or ethnic groups with darker skin, and persons with less sun exposure, including persons who live in higher latitudes in winter, nursing home residents and health care workers, which also have higher risk of COVID-19. COVID-19 is less common in populations with more vitamin D intake – pregnant women, children and persons who eat more fish. Analyzing internal data at the University of Chicago Medicine, we found that the risk of testing positive for COVID-19 is 77% higher for vitamin D deficient persons who are not treated. Several studies find COVID-19 outcomes are better with higher vitamin D levels.

Experimental studies of vitamin D in COVID-19 are needed, especially since efforts to treat some infectious or inflammatory diseases with vitamin D have failed. Negative findings have been attributed to vitamin D doses that are too low, infrequent or do not account for baseline vitamin D levels, dietary sources or sun exposure. Dose is important; the recommended daily allowance (RDA) of 600 IU/day and minimum sufficient level (30 ng/ml) are based on bone health, not immune function, for which needs are unknown. The Institute of Medicine (IOM) has recommended 4,000 IU/day as safe for broad consumption, noting the lack of clear evidence of benefit and some evidence of toxicity at higher doses, including hypercalcemia and resulting falls in older persons. They also noted that vitamin D supplements are often variable in dosing. For example, even the US Pharmacopoeia standards for vitamin D, which likely exceed usual practice, specify variation from 90% to 165% of the stated dose. Notably, however, side effects are rare even with 10,000 IU/day, and humans evolved with sun exposure expected to produce 25,000 IU/day. Vitamin D levels in lifeguards are 50-100 ng/ml. Light skin and different vitamin D binding globulin in persons of northern European origin compared to populations more recently from equatorial regions may reflect evolutionary pressures related to sunlight and vitamin D in northern latitudes and may explain increased rates of vitamin D deficiency in Black and Latinx populations, and perhaps increase COVID-19 risk, which is 1.5-4 times greater for Black and Latinx Chicagoans than for White Chicagoans. Experimental studies of vitamin D in diverse populations are urgently justified.

In this context, *the proposed study is innovative most importantly because it proposes to perform a randomized clinical trial to prevent COVID-19.*

**II. Purpose:**

Our overall aim of this study is to perform a randomized clinical trial (RCT) in a diverse, largely minority, cross-section of at least 2,000 US residents to test the hypothesis that vitamin D supplementation with 4,000 IU/day compared to minimal supplementation with 400 IU/day will decrease COVID-19 incidence (primary outcome) and adverse health outcomes (secondary outcome).

Primary Outcome: patient report of lab-confirmed COVID-19 (and date). Secondary Outcomes: patient report of hospitalization (and date), ICU use, mechanical ventilation, death, patient-reported adherence to vitamin D supplementation, and results of COVID-19 antibody blood spot tests. Key milestones for success will include partner and participant recruitment, including intake surveys, baseline Vitamin D levels and antibody testing for 20% of the sample, vitamin D distribution to the participants, completion of quarterly surveys, end-of-study antibody testing for full sample, and analysis and publication of the study results.

**III. Description of protocol methodology:*****Summary***

Our RCT will test the hypothesis that vitamin D supplementation with 4,000 IU/day compared to minimal supplementation with 400 IU/day will decrease the primary outcome of COVID-19 incidence and secondary outcomes of COVID-19 adverse health outcomes (hospitalization, ICU use, mechanical ventilation and death) in a diverse, largely minority, sample of 2,000 US residents. It has been developed and will be implemented in partnership with key community stakeholders in Chicago and other US cities.

We propose the 4,000 IU/day higher dosage because it is the highest dose the IOM recommended as safe to consume without clinical supervision and we wish to maximize the likelihood of enhancing immune function while minimizing risk of harm in the absence of clinical supervision so the intervention can be broadly scaled at low cost. Based on needs for bone health, the NIH and IOM recommend 600–800 IU/day as adequate for 97.5% of people, so we have chosen the low dosage to be the amount in most multivitamins (400 IU, 2/3 of the RDA), instead of placebo. This ensures almost all participants have total vitamin D intake (including diet) that meets the RDA. As participants might alter their adherence to vitamin D or personal protective guidelines if they knew the dose to which they had been randomized, we propose a blinded-research design.

We will target recruitment of a population that has a high fraction of racial minorities and socioeconomically disadvantaged individuals since these populations have been disproportionately impacted by COVID-19. Latinx and Black residents each constitute about 1/3 of Chicago's population and have COVID-19 incidence (5,626/100,000 and 2,845/100,000, respectively), 1.5-4 times that of White Chicagoans (2,115/100,000). COVID-19 mortality differentials by race are even higher. Moreover, 75% of Black and Latinx persons in the US are vitamin D deficient. Targeting these populations is important most critically because of their urgent needs for interventions to address COVID-19 but also because the high incidence of both COVID-19 and vitamin D deficiency in Chicago's racially and ethnically diverse population and known northern location make it a scientifically advantageous place to assess the potential benefits of vitamin D supplementation in COVID-19.

Study recruitment will be conducted online to minimize COVID-19 exposure, with vitamin D distribution primarily delivered by mail to participants' home addresses or by pick-up from community partner locations. Supported by student volunteers and cost-shared staff effort as needed, we will partner with Chicago community organizations to promote and disseminate information about the study to their clients/members during a 2-month promotional campaign. We have established community partners in the Black and Latinx community through our prior work that we will engage as delineated below under Partner Engagement. Promotion and information-sharing strategies will vary by partner, but we expect that, at minimum, partners will send communications to encourage participation and share information about eligibility criteria and how to enroll in the study. The study website will also list pick-up sites for interested participants. Interested participants will be guided to a secure REDCap platform that will provide information about the study and allow

them to virtually enroll and consent to the study, using their email address for enrollment and later survey participation. Enrollment will require completing a 15-minute baseline survey in REDCap that asks about demographics, health and health behaviors (including vitamin D intake and sun exposure), COVID-19 risks. Persons reporting health conditions indicating risk from vitamin D treatment (hypercalcemia, hyperparathyroidism, kidney stones, pregnancy, lactation) or an allergy to vitamin D will be excluded.

Due to lower than anticipated enrollment in both this study and our other NIH Vitamin D study (IRB20-1302), we will merge study populations. Participants graduating from the 6-month NIH study will be contacted via email and offered the opportunity to participate in this study. These “transitional” participants will then be directed to a new consent form to be enrolled in this study. For participants that have graduated from the NIH study prior to the approval of this amendment (amendment #24 for #IRB20-0847), the study team will reach out via email to invite them to participate. These previous graduates will be considered new participants and will complete the same eligibility screening, consent, and baseline survey process as other new participants.

A minimum of 2,000 eligible participants will be randomized to the 400 IU/day or 4,000 IU/day treatment arms. Each lot of vitamin D supplements will be tested to ensure they are within the dosing tolerance that meets USP standards. Transitional participants will maintain their dosing arm from the previous NIH study; those in the high or moderate dosing arms (10,000 IU/day or 4,000 IU/day) will receive 4,000 IU/day and those who were previously in the low arm (400 IU/day) will receive 400 IU/day. The UCM pharmacy will prepare and package blind-label safety-top medication bottles to be distributed to participants via mail to either their home address or for pick-up from community partners. During the 12-month implementation period, we will ask participants to complete follow-up surveys every 3 months. A sample of the participants (20%) who complete the surveys also have the opportunity to receive a free home COVID-19 antibody blood spot test and Vitamin D level tests at the beginning of the study. Both tests are done at home by the participant themselves. Testing this subset will allow the research team to capture baseline levels of Vitamin D and immunity to COVID-19. We suspect 10% will have positive antibodies and 80-90% will be Vitamin D deficient; these baseline sample tests will confirm the general hypothesis. Originally, we planned for the entire sample to be offered the opportunity to receive a free, in home COVID-19 antibody blood spot tests at the end of the study. Due to low return rate, we paused end of study testing in early 2024 and now wish to permanently discontinue it. Over the course of this three year study, it is likely that most participants have COVID-19 antibodies, therefore testing is no longer scientifically valuable. Results of the antibody test will help inform research outcomes and may increase completion of quarterly self-reported surveys.

In addition to these questions, we have added some questions on the baseline and follow-up surveys that evaluate sleep habits as well as additional possible risk factors for COVID-19 outcomes. These risk factors—hypertension, diabetes, and mood—are shown to have possible linkages to vitamin D levels. These factors are receiving increased attention in the context of COVID-19 risk and its relationship to low vitamin D levels. While available evidence suggests there is a link between hypertension/cardiovascular disease, diabetes and metabolism, depression/anxiety, and vitamin D levels, to-date no causal relationship has been established. This is supported by both evidence as recently as this year, as well as earlier studies. Questions about hypertension and diabetes are of our own construction, and questions about depression and anxiety come from validated instruments, the GAD-2 and the PHQ-2. We hope to shed light on the relationship between our outcomes of interest, vitamin D, and these risk factors by asking subjects, both already enrolled and new, about these factors.

Our data management plan will specify procedures to collect, organize, handle, clean, analyze, describe, preserve, destroy, report and share data. We will review self-reported survey data regularly to prevent and monitor missing data. We will record and report all known reasons for study dropout and missing data. For our primary outcome of COVID-19 infection as measured by patient report of clinically confirmed COVID-19 (or viral PCR if available) and COVID-19 seroconversion tests that data collection, hazard models will be used to assess the effect of vitamin D dosing on the outcome. We will first develop hazard ratios for between-group analyses on the primary outcome using log-rank tests, and then Cox proportional hazard models with covariates including vitamin D dose, age, gender, race, ethnicity, sun exposure, exposure of cohabitants,

employment status, and geographic location. Secondary study outcomes of hospitalization, ICU use, mechanical ventilation use and death will be analyzed with longitudinal mixed models with these covariates.

We estimate statistical power using a simulation model based on conservative estimates of the fraction of Chicagoans already immune but unaware they have had COVID-19 ( $\leq 10\%$ ), monthly incidence of COVID-19 (3%/month for Black and Latinx persons and 1%/month for White persons), size of the true effect of vitamin D on incidence we seek to assess, confidence we wish in that assessment, and length of time participants are followed. Based on this we propose to recruit at least 2,000 participants, yielding 80% power at  $p < 0.05$  to demonstrate a reduction of 20% or more in COVID-19 incidence due to vitamin D within 12 months of randomization.

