#### **XI. Monitoring of safety:**

The current study represents a single-site clinical trial in which the risks inherent to the intervention are of minimal risk to participants given the long-standing use of vitamin D supplementation with few adverse events. The protocol's exclusion criteria and monitoring plan limit the likelihood that subjects will develop a severe medical condition during the course of this study. Commensurate with these risks, the PI [name], with support from the Clinical Advisory Committee and co-investigator [name], will incorporate this study into an already established formal Data and Safety Monitoring Board (DSMB). Given the low reported COVID rates and low reported rates of potential side effects from vitamin D treatment, we will utilize the DSMB we have already convened for our NIH Vitamin D study (IRB20-1302), which currently meet quarterly. This independent DSMB has been set up and is comprised of three experts, a Chair and two members, who have been providing regular oversight for that study. These individuals are senior faculty members and hold expertise in clinical trial oversight and design, biostatistics, endocrinology, pulmonology and critical care medicine. Further, these individuals are the same experts we identified in the DSMB Charter below.

To date, the NIH DSMB has met twice, once in June 2021 and again in August 2021, and has identified no patient safety concerned (note the NIH study includes the same doses as Vitamin D as this study, as well as one arm with a higher dose of 10,000 IU per day). We plan to bring more data analysis from this study to next quarterly joint-DSMB In December 2021. We believe this is justified given the absence of any evidence of adverse outcomes in this study to date. In addition, due to lower than anticipated enrollment and the studies being so complementary, we plan to eventually combine the two studies samples at a later date and will submit additional amendments to reflect this change. In the meantime, introducing this study to the existing DSMB is one of the first steps of merging these studies.

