Primary analysis: We will use a multivariable Cox proportional hazards regression model to estimate an adjusted hazard ratio of the effect of moderate versus low dose vitamin D on the outcome. Covariates will include age, sex, race and ethnicity, baseline sun exposure, baseline insomnia severity, baseline COVID-19 exposure outside work, baseline employment, randomization date, and baseline geographic location. The selection and coding of these covariates mirror a prior NIH-funded trial of vitamin D and COVID-19 (NCT04868903). Coding of these covariates include age (continuous), sex (male versus female), race and ethnicity (non-Hispanic White versus non-White or Hispanic), sun exposure (average \leq 30 minutes per day versus $>$ 30 minutes per day), insomnia severity (no or subthreshold insomnia versus moderate or severe insomnia), COVID-19 exposure outside work (no versus yes), and employment (no versus yes). Non-Hispanic White participants will be defined as those who report White race and non-Hispanic or Latino ethnicity. Non-White or Hispanic participants will be defined as those who report either non-White race or Hispanic or Latino ethnicity. Whereas recruitment in the NIH trial was limited to Chicagoland and stratified by recruitment site (UChicago Medicine and Rush University Medical Center), this study recruited participants across the United States, such that we will include baseline geographic location as a covariate, defined by baseline mailing address latitude $<$ 40.0 or \geq 40.0 degrees. Furthermore, whereas the NIH trial recruited participants who concluded their participation prior to when Omicron arrived in Chicago about December 1, 2021, every participant in this study could be active in the study after Omicron arrived in the United States about December 1, 2021. Rather than control for randomization date with a linear time trend and an indicator variable for potential participation after Omicron arrived like the NIH trial, we will control for randomization date with a series of thirteen quarters defined by calendar quarter and year (Q1 2021 [December 2020 through March 2021], Q2 2021 [April 2021 through June 2021], Q3 2021 [July 2021 through September 2021], Q4 2021 [October 2021 through December 2021], Q1 2022 [January 2022 through March 2022], etc. up to Q1 2024 [January 2024 through April 2024]).

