Secondary analysis of non-Hispanic White participants living north of 40.0 degrees: We will use a multivariable Cox proportional hazards regression model to estimate an adjusted hazard ratio of the effect of moderate versus low dose vitamin D on the outcome in participants who are non-Hispanic White and whose baseline mailing address latitude is \geq 40.0 degrees. Covariates will mirror those described in the primary analysis, excluding race and ethnicity and baseline geographic location. We prespecify this secondary analysis prior to unblinding because

the NIH trial cited above found stronger evidence of increased time to first COVID-19 infection with vitamin D supplementation among non-Hispanic White participants, and participants in that trial were recruited in the Chicagoland area which has a latitude north of 40.0 degrees. The NIH trial also found stronger evidence of increased time to first COVID-19 infection with vitamin D supplementation among participants who reported an average of ≤ 30 minutes of sun per day.

Additional Analyses

Time-varying analysis: We will use a time-varying, multivariable Cox proportional hazards regression model to estimate an adjusted hazard ratio of the effect of moderate versus low dose vitamin D in each calendar quarter (Q1: January through March, Q2: April through June, Q3: July through September, Q4: October through December) on the outcome in participants whose baseline mailing address latitude is ≥ 40.0 degrees. Covariates will mirror those described in the primary analysis, with the addition of four calendar quarter indicator variables as time-varying covariates. Furthermore, instead of using a single indicator variable for moderate dose vitamin D, we will include four indicator variables for treatment with moderate dose interacted with the time-varying calendar quarter. The reference group for the uninteracted and interacted time-varying calendar quarter indicator variables will be Q1 for low dose vitamin D.

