Missing Data: Assuming missingness at random, we will impute missing values of covariates with multiple imputation by chained equations with 20 imputations. Covariates in the imputation will include the covariates in the primary analysis excluding moderate dose vitamin D. The imputation for the secondary analysis of non-Hispanic White participants living north of 40.0 degrees and the treatment heterogeneity analysis will be performed among the denominator of all participants in the primary analysis.

Statistical Significance and Multiple Testing: Statistical significance will be determined by $p < 0.05$ for the primary analysis and the secondary analysis of non-Hispanic White participants living north of 40.0 degrees with no adjustment for multiple comparisons.

Software: Data analysis will be executed in Stata 18.0.

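### Prior NIH-study participants enter this trial by two routes, but the SAP neither identifies them nor checks whether they alter the result

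*Protocol*

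**What the plan says.** **Two entry routes.** Section III of the protocol merges the populations of this trial and the NIH study (IRB20-1302) because both enrolled slowly.

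- *Transitional participants* move over as they finish the 6-month NIH study. Sections III, V and VII have them keep their NIH arm: former 10,000 and 4,000 IU/day participants receive 4,000, and former 400 IU/day participants receive 400. Section VIII lets their last NIH survey stand in for a new baseline survey.
- *Earlier graduates* finished before amendment #24. Of them Section III says: "These previous graduates will be considered new participants and will complete the same eligibility screening, consent, and baseline survey process". Section VIII and Appendix A repeat this. No sentence says outright that they are randomized again. That follows by implication, because only transitional participants keep an arm.

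**Nothing addresses earlier trial dosing.** Exclusion 8 in Section VIII concerns vitamin D being taken at enrollment on professional advice, or D2. Section VI concerns other supplements when study supplements start. Section IX lists baseline vitamin D level as a Cox covariate, but Section III plans that test for 20% of the sample, and the SAP's primary model omits it.

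**The SAP mentions neither group.** Its primary model, subgroup list and imputation model contain no term for prior NIH participation. As written, both groups are pooled with new participants.

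**The secondary test comes from NIH results.** The SAP tests non-Hispanic White participants at or above 40.0 degrees latitude because "the NIH trial cited above found stronger evidence of increased time to first COVID-19 infection with vitamin D supplementation among non-Hispanic White participants". On thresholds it says: "Statistical significance will be determined by $p < 0.05$ for the primary analysis and the secondary analysis", without multiplicity adjustment.

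**The concern.** Three separate things are at stake.

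1. **Dilution.** A former 4,000 or 10,000 IU/day graduate can be a 400 IU/day control. Any lasting effect of the earlier dose then narrows the contrast. The protocol's own rationale makes this relevant. Its Background attributes some earlier negative trials to ignoring baseline levels, and cites a 70% reduction in respiratory infection in deficient persons against 10% in sufficient ones. Section III expects 80-90% of participants to be deficient at baseline, and recent graduates of the higher NIH arms may not fit that premise.
2. **Non-randomized allocation.** Transitional participants were not randomized in this trial, and two NIH arms collapse into one, so their split may not be 1:1. The SAP also starts the clock at randomization without saying which date that is for them.
3. **Confirmation.** The SAP describes NIH recruitment as limited to Chicagoland, north of 40 degrees. A non-Hispanic White NIH participant who re-enters and has not moved south falls into the secondary subset. A reader cannot see how much of that subset consists of people who contributed to the finding being re-examined.

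**Working it through.** **Step 1. The plan's own power figure.** Protocol Section III credits its target sample of 2,000 with a power of 80% at the 5% level. The stated aim is "to demonstrate a reduction of 20% or more in COVID-19 incidence due to vitamin D within 12 months of randomization". Inputs: "3%/month for Black and Latinx persons and 1%/month for White persons", and up to 10% already immune. The planned race mix, the sidedness, and whether 20% means risk or hazard are not stated, so 80% can be neither confirmed nor refuted. Take 1,000 per arm, all at 3%/month, 10% immune:

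- Control 12-month risk = 0.9 × (1 − 0.97^12) = 0.2755.
- Read as a 20% cut in risk (to 0.2204), two-sided power is 81.5%.
- Read as a hazard ratio of 0.8, treated risk = 0.9 × (1 − 0.97^9.6) = 0.2282. Events = 1,000 × (0.2755 + 0.2282) = 504. Schoenfeld power = Φ(√504/2 × |ln 0.8| − 1.96) = 70.7%.

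The hazard-ratio version matches the SAP's Cox model and is the base case below. It is generous on event numbers: with two thirds Black/Latinx and 10% immune, the same formula gives 397 events and 60.4% power, against 631 events needed for 80%. The point does not depend on which version was meant.

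**Step 2. Dilution by re-randomized graduates.** Not in the documents, so assumed:

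- graduates are a share f of the sample;
- two thirds of them had 4,000 IU/day or more (equal NIH arms);
- those now on 400 IU/day keep the full benefit (hazard × 0.8) for m months;
- prior dosing adds nothing in the 4,000 IU arm.

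Risk in an affected control = 0.9 × (1 − 0.97^(12 − 0.2m)). Control-arm risk c = (1 − 2f/3) × 0.2755 + (2f/3) × affected risk. Diluted HR = ln(1 − 0.2282/0.9) / ln(1 − c/0.9).

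Example, f = 20%, m = 12: the affected share is 0.20 × 2/3 = 13.3% of the 400 IU arm. c = 0.8667 × 0.2755 + 0.1333 × 0.2282 = 0.2692; events = 497; HR = 0.8226; power = Φ(√497/2 × |ln 0.8226| − 1.96) = 58.6%.

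| Graduates (f) | m = 3: HR, power | m = 6: HR, power | m = 12: HR, power |
|---|---|---|---|
| 0% | 0.800, 70.7% | 0.800, 70.7% | 0.800, 70.7% |
| 5% | 0.801, 70.0% | 0.803, 69.3% | 0.806, 67.8% |
| 10% | 0.803, 69.3% | 0.805, 67.9% | 0.811, 64.8% |
| 20% | 0.805, 67.9% | 0.811, 64.9% | 0.823, 58.6% |
| 30% | 0.808, 66.5% | 0.817, 61.9% | 0.834, 52.1% |

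Every entry moves toward 1.

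**Step 3. False positives and dependence on the NIH result.** A simulation with no vitamin D effect in either study used 20,000 runs, 800 people in each, and persistent individual risk (frailty variance 1). Overlapping people made up 20% or 50% of this trial's subset.

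| Overlapping people | Correlation with NIH z-statistic | Type I error here |
|---|---|---|
| Re-randomized | 0.00-0.01 | 0.050-0.051 |
| Keep NIH arm | 0.03-0.05 | 0.050-0.051 |

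**Step 4. Transitional allocation.** If the NIH arms were equal (an assumption), the split is 2:1. If transitional participants were 10% of the sample and everyone else split 45/45, they would be 6.67/51.67 = 12.9% of the 4,000 IU arm and 3.33/48.33 = 6.9% of the 400 IU arm. Entry route would then be associated with arm, and the SAP model has no route term to absorb a difference in risk between routes.

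**The case against.** The strongest reply is that the gap has modest consequences and that firmer readings outrun the text. Four readings that a reader might infer are not supported.

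- *That carry-over is established.* The documents give no number of graduates, gap since the last NIH dose, persistence or NIH allocation ratio. Carry-over is possible, not shown. Even with full benefit retained, a 5-10% graduate share costs about 0.7 to 6 power points.
- *That prior dosing confounds the arms or could create a false positive.* For re-randomized graduates, prior dose is independent of the new arm. The effect is dilution only.
- *That the secondary test is statistically dependent on the NIH trial.* A fresh assignment is independent of the earlier result even in the same person. Arm-keeping participants add only a small correlation. The SAP never calls the analysis a replication or an independent check; it says only that NIH findings motivated it. What remains is narrower: shared people limit how far the result generalizes as confirmation.
- *That earlier graduates must be a large group.* The SAP says "the NIH trial recruited participants who concluded their participation prior to when Omicron arrived in Chicago about December 1, 2021", and Section XI, describing the position before the December 2021 board meeting, still says "we plan to eventually combine the two studies samples at a later date and will submit additional amendments to reflect this change". That suggests most NIH participants finished before any merger. But the SAP also says that the NIH trial used an indicator for potential participation after Omicron arrived, which conflicts with all of them having finished. Amendment #24 is undated in the text, and both studies under-enrolled. The split between routes cannot be deduced.

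It is also fair that the trial admits people with other past supplement use, which randomization is expected to balance. That argument covers earlier graduates, if they are re-randomized. It does not cover transitional participants, whose arm was fixed elsewhere. The omission from the SAP stands for both groups.

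**Conclusion.** The concern holds as a gap in the analysis plan. Two groups with prior trial dosing enter, one of them not randomized in this trial, and the SAP cannot show whether they matter.

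For earlier graduates the risk is a hazard ratio nearer to 1 and lost power: in the assumed base case, from under 1 point (5% graduates, 3 months) to about 19 points (30%, 12 months of full carry-over). The true value could be nil. This rests on their being newly randomized, which is inferred.

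For transitional participants the risk is an allocation that may differ from 1:1. A 2:1 split follows only if the NIH arms were equal.

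The limit on the secondary test as confirmation rests on the SAP's NIH trial (NCT04868903) being the protocol's IRB20-1302 study. That is likely but not stated. If they differ, that part falls and the rest stands.

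The change should be made, but nothing here shows the primary analysis to be invalid.

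**What to change.** Amend the SAP before unblinding:

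1. Prespecify a sensitivity analysis of the primary model that excludes all prior NIH participants, whichever route they took.
2. Run the secondary analysis in participants with no prior NIH participation and report the inclusive version alongside it, or the reverse, with the order fixed in advance.
3. Add entry route (new, earlier graduate, transitional) to the primary model as a covariate or stratum. Do not use prior dose as a main effect: it would not remove dilution among re-randomized graduates, and among transitional participants it determines the current arm.
4. Report counts by route, prior NIH arm and time since last NIH dose.

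The same text should confirm that earlier graduates are randomized afresh, state which date starts the clock for transitional participants, and say whether the SAP's NIH trial is IRB20-1302.

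The cost is SAP wording and a flag from the sponsor's own NIH-study records. Dosing and enrollment do not change. The downside is a smaller sample and lower precision in the restricted analyses, most of all in the secondary subset, where the overlap is likely to be concentrated.
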